7.7 Biomarkers assessment

Blood samples will be taken from a peripheral vein at admission, 72 hours, 14 days and 3, 6 and 12 months.

One EDTA-containing tube, one SST containing tube, one Serum Separator Clot Activator tube and one PPT tube will be used for analysis of plasma levels of biomarkers by the True Health Diagnostics LLC, Richmond, VA.

One sodium heparin tube will be used to analyze cytokines markers.

7.8 Study Schedule

	Inpatient:	Inpatient: 72 hours	Outpatient Visit 1: 14 days	Outpatient Visit 2: 3 months	Outpatient Visit 3: 6 months	Outpatient Visit 4: 12 months
Screening *	х					
Consent	X					
Clinical assessment **	X	X	X	X	X	X
Investigational therapy	X	X	X			
Echocardiogram	X					X
СВС		X	X			
hs-CRP	X	X	X	X	X	X
Biomarkers	X	X	X	X	X	X

^{*} Pregnancy test will be performed, if indicated

When feasible, results from clinically indicated studies will be used.

^{**}_Clinical assessment includes history and physical, medication reconciliation, and assessment of adverse events

Inpatient samples will be taken upon enrollment, at 72 hours (± 12 hours [or more if patient discharged before 60 hours]).

Samples will be centrifuged and then refrigerated, and shipped with cold pacs within 24 hours to True Health Diagnostics LLC, Richmond, VA. The results will be sent to the PI at VCU and to each center by email or fax.

Outpatient visits will be scheduled at 14 days (± 2 days), 3 months (± 2 weeks), 6 months (± 2 weeks), and 12 months (± 2 weeks).

7.9 Cost coverage analysis

A cost coverage analysis will be conducted in each center prior to the initiation of the trial to determine what constitutes standard of care, which will be billed to the patient or the insurer, and what is considered 'research' which will be paid for with the study budget.

8) ASSESSMENT OF SAFETY

8.1 Specification of Safety Parameters

Safety parameters will include data deriving from history and physical examination performed at each visit, laboratory data and results of functional and imaging tests. To enhance detection of adverse events between visits, all patients will be encouraged to contact the research team at any time with concerns or any perceived changes in their healthcare status.

Disease-related data (MI- and HF-related) will be assessed including changes in symptoms (or new symptoms), functional capacity, vital signs (including weight), renal function, or any significant changes in medications.

Data specific to the treatment will also be assessed. The patient will be asked about symptoms and examined for signs of infection. Considering that anakinra may mask signs of infection such as fever, a low threshold for further investigation will be advocated. A complete cell count will be measured at 72 hours and 14 days to exclude the unusual cases of anakinra-related neutropenia (ANC<1,000/mm³), for which suspension of active treatment will be encouraged until return to a value of ANC>1,800/mm³ (or >1,000/mm³ if patient is African-American).

Changes to treatment for side-effects or unanticipated problems will be performed without breaking the randomization code, unless deemed necessary for the treatment of the individual patient by the physician, in which case the physician will be made aware while the remainder of the team, especially the investigators performing and interpreting the tests, will be maintained blinded.

The risks of the tests performed have been described above. In order to reduce risk, the procedures will be performed by skilled practitioners in the standard clinical fashion.

Abnormal or incidental findings will be handled on a case by case basis as clinically indicated.

8.2 Data collection

The principal investigator at each site will be provided with a data collection sheets or case report forms on which data about the individual subject will be collected. The subjects will be identified as a consecutive number in each center (i.e. A01, A02, ...A08; B01, B02, ... B08; C01). The data collected on these forms will not contain any personal identifiable information. The forms will be transmitted to the coordinating center at VCU through either a secure HIPAA compliant fax line or email correspondence, or hand-delivered. A centralized database of deidentified data will be held at VCU.

8.3 Methods of Timing for Assessing, Recording, and Analyzing Safety Parameters

8.3.1 Adverse Events

All Adverse Effects (AEs) will be recorded on an AE form regardless of causality.

An AE is defined as any untoward medical occurrence in a patient or clinical investigation subject administered a pharmaceutical product considered to causally related to the study treatment or research conduct. An AE can therefore be any unfavorable and unintended sign (including an abnormal laboratory finding), symptom, or disease temporally associated with the use of medicinal (investigational) product. The occurrence of an AE may come to the attention of study personnel during study visits and interviews of a study recipient for medical care, or upon review by an investigator or study coordinator. An event that is considered by the investigator(s) to be expected and related to the natural history of the disease is NOT considered an AE.

All events considered AEs including local and systemic reactions not meeting the criteria for "serious adverse events" will be reported on the appropriate AE form. Information to be collected includes event description, time of onset, clinician's assessment of severity, relationship to study intervention (assessed only by those with the training and authority to make a diagnosis, which would include a physician) and time of resolution/stabilization of the event. All AEs occurring while on study must be documented appropriately regardless of relationship. All AEs will be followed to adequate resolution.

Any medical condition that is present at the time that the patient is screened should be considered as baseline and not reported as an AE. However, if it deteriorates at any time during the study, it should be recorded as an AE.

All AEs must be graded for severity and relationship to study product.

Severity of Event: All AEs will be assessed by the clinician according to the following guidelines to quantify intensity:

 Mild: events require minimal or no treatment and do not interfere with the patient's daily activities.

- Moderate: events result in a low level of inconvenience or concern with the therapeutic measures. Moderate events may cause some interference with functioning and may require systemic drug therapy or other treatment.
- Severe: events interrupt a patient's usual daily activity and may require systemic drug therapy or other treatment. Severe events are usually incapacitating.
- Life threatening: any adverse drug experience that places the patient or subject, in the view of the investigator, at immediate risk of death from the reaction as it occurred (i.e. does not include a reaction that might have caused death had it occurred in a more severe form).

Changes in the severity of an AE will be documented to allow an assessment of the duration of the event at each level of intensity to be performed. Adverse events characterized as intermittent require documentation of onset and duration of each episode.

Relationship to the intervention: All suspected AEs must have their relationship to study intervention assessed using the terms: associated or not associated. In a clinical trial, the study intervention must always be a suspect. To help assess, the following guidelines are used to assess causality:

- Definitely related: The event is temporally related to the administration of the study intervention and, in the opinion of the investigator, no other etiology explains the event.
- Probably related: The event is temporally related to the administration of the study intervention and represents, in the opinion of the investigator, the most plausible explanation of the event.
- Possibly related: The event is temporally related to the administration of the study intervention but, in the opinion of the investigator, it does not represent the most likely explanation of the event.
- Definitely Unrelated: The event is temporally independent of study intervention and/or the event appears, in the opinion of the investigator, to be explained by another etiology.

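### Section 8.3.1 contradicts itself on whether an adverse event must be causally related, and its causality levels overlap, so infections can be coded inconsistently and be missing from AE counts

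*Combined protocol and SAP*

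**What the plan says.** Section 8.3.1 opens by saying that adverse events "will be recorded on an AE form regardless of causality". The definition that follows covers an untoward occurrence in a subject "administered a pharmaceutical product considered to causally related to the study treatment or research conduct". The next sentence allows any unfavourable sign, symptom or disease with a temporal association to the product, and a later one requires AEs to be documented whatever their relationship.

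The part on relationship to the intervention asks for each suspected AE to be "assessed using the terms: associated or not associated", then lists four levels: definitely, probably and possibly related, and definitely unrelated. Possibly related means that the event is temporally related "but, in the opinion of the investigator, it does not represent the most likely explanation of the event". Definitely unrelated means that it is "temporally independent of study intervention and/or the event appears, in the opinion of the investigator, to be explained by another etiology".

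The event form in Appendix C has tick-boxes for infection and for sepsis or severe infection, a separate yes/no box for adverse event, and four relationship boxes, one of them for unrelated. Under section 8.6 the DSMB coordinator supplies data on screening, enrolment, adverse events and withdrawals.

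**The concern.** Infection is a named risk of anakinra in the background section, which describes the infections as mainly upper respiratory and generally mild. Section 8.1 adds that the drug may mask fever. An excess of common, mild infections is best seen by counting all of them by arm, because a single case may have another plausible explanation. Such a count needs a rule that every site applies in the same way and that does not depend on attribution. Section 8.3.1 gives two conflicting rules for what is an AE, and two levels of relationship that can both apply to one event. At stake are the consistency of infection coding across the three sites and the completeness of the AE counts that the DSMB sees while the trial is running.

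**Working it through.** No arithmetic applies to the defect itself. It is checked by comparing the sentences and then following an infection through the recording routes.

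1. **Is causal relation required for an AE?** The definition says yes ("considered to causally related to the study treatment or research conduct"). Three other sentences in 8.3.1 point the other way: recording regardless of causality, temporal association as enough, and documentation regardless of relationship. The scale points the other way too, since under the causal clause an AE rated definitely unrelated could not exist. The two sentences that use 'regardless' govern events already called AEs, so read literally they cannot bring back an event that the definition excludes. The section is self-contradictory rather than plainly restrictive.

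2. **Are the levels exclusive?** Take a pneumonia on day 6 of the 14 dosing days in a patient with chronic lung disease, where the investigator thinks the lung disease the likelier cause.
   - Possibly related: there is a temporal link and the drug is not the most likely explanation. Met.
   - Definitely unrelated: the event is not temporally independent, but the investigator can regard it as explained by another etiology, and 'and/or' makes that enough. Met.
   
   Both codes follow the text.

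3. **Does the two-term rating settle it?** No. Nothing says which of the four levels count as associated. Possibly related would naturally be associated and definitely unrelated not associated, so the same pneumonia can fall on either side.

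4. **Where is an infection judged unrelated recorded?**
   - Section 8.1: patients are asked about symptoms and examined for infection. This finds cases but does not classify them.
   - Event form: the infection box has no causality condition, so the event is written down. The separate AE box can be marked no, and the causal clause gives grounds for that.
   - Section 8.6: the DSMB coordinator supplies adverse events. An infection marked as not an AE need not be among them.
   - Section 8.3.2: an SAE is first an AE, so SAE reports inherit the ambiguity.
   - Sections 9.1 to 9.3: adjudication covers sepsis or other serious infection requiring antibiotics, takes place at the end of the study and has no effect on its conduct. It does not cover mild infections and does not protect ongoing monitoring.

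The remaining gap is a non-serious infection, judged unrelated, that is on the form but not in the AE counts.

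**The case against.** The strongest reply is that the causal phrase is ungrammatical, is outnumbered by sentences saying the opposite, and is contradicted by the unrelated box on the form, so sites would sensibly ignore it. Section 8.3.1 also says "In a clinical trial, the study intervention must always be a suspect", which steers doubtful on-treatment events towards possibly related, and it offers the levels as guidelines. Being explained by another cause is a stronger statement than the drug not being the most likely cause. All of this stands as far as it goes: many investigators will code sensibly, and not every possibly related event will also look definitely unrelated. It does not remove the conflict, because a site that follows the definition literally is also following the protocol.

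Three stronger readings might be inferred, and the documents do not support them.

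- **Infections drop out of the safety data.** They are actively sought (8.1), ticked on the event form, adjudicated if serious (9.2), and recorded as a reason for stopping treatment if systemic (10.1). Section 3b of the DSMB charter has the board review other safety data as well as AE data. What can be lost is the AE count, not the record.
- **A difference between arms would be hidden.** The documents do not say what share of infections would be attributed to another cause, and blinded attribution would remove placebo infections as well. If 25% and 15% are assumed purely for illustration, Fisher's exact test at the two-sided 0.025 level has about 6% power with 33 against 33 patients, and about 10% with 66 against 33, even if every infection is counted. Sample size would be the main reason for missing such a difference.
- **The scale decides the 7- and 15-day reporting limits.** In 8.3.2 and 8.7 those limits govern the forwarding of reports to the funder. The prompt report to the IRB and DSMB turns on whether the SAE is unexpected, and nothing ties the word 'suspected' to the four levels.

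**Conclusion.** The point holds as a contradiction within 8.3.1 together with overlapping, unmapped causality levels. The consequence is limited. The same infection can be coded differently between sites, and a non-serious infection judged unrelated can be missing from the AE counts given to the DSMB while remaining on the event form. No number of affected events can be derived from the documents. The conclusion assumes that some investigators apply the causal clause or the 'or' branch as written, and that the DSMB's AE tables are built from events marked as AEs; no separate infection table is specified. It is worth correcting because infection is a named risk of the drug and the correction is cheap.

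**What to change.** In section 8.3.1:

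- Delete "considered to causally related to the study treatment or research conduct" from the AE definition.
- Make the levels exclusive. Reserve 'unrelated' for events with no reasonable possibility of a causal role, for example no plausible temporal link, or clearly and fully explained by another cause. Rate all other temporally related events at least possibly related. Changing 'and/or' to 'and' would not be enough: a temporally independent event of unknown cause would fit no level, and an on-treatment event with an obvious other cause, such as a traffic injury, would have to be called possibly related.
- State that definitely, probably and possibly related map to associated, and unrelated to not associated.

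For monitoring, tabulate all infections recorded on the event form by arm for the DSMB, whatever their attribution and whatever is marked in the AE box.

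The cost is a few wording changes and one more DSMB table. The event form already has the four relationship boxes, and section 7.2 allows access to the randomization log when the DSMB indicates it. The downside is somewhat more AE forms and more events coded possibly related.

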8.3.2 Serious Adverse Events

An SAE is any adverse event/experience occurring between baseline assessments and the patients final study visit that results in any of the following outcomes and is considered by the investigator(s) to be unexpected or not consistent with the natural history of the disease:

- Death
- Life threatening (subject at immediate risk of death)
- Requires inpatient hospitalization or prolongation of existing hospitalization
- Results in a persistent or significant disability or incapacity
- Important medical events that may not result in death, be life threatening, or require hospitalization may be considered SAEs when, based upon appropriate medical judgment, may jeopardize the subject and may require medical or surgical intervention to prevent one of the outcomes listed in this definition.

All the unexpected SAE will be promptly (within 24 hours) reported to the local IRB and DSMB (see reporting procedures). The DSMB report to the investigators will be forwarded to the NHLBI Program Officer, including the discussion of the concerns, and the basis for any recommendations that the DSMB has made in response to the concerns (within 7 calendar days if fatal or life-threatening unexpected, suspected serious adverse reactions; or within 14 days for unanticipated problem that is not an SAE or within 15 calendar days for all non-fatal, non-life threatening unexpected, suspected serious adverse reactions, or within 30 days of receipt of the DSMB or IRB report for all other unanticipated problems or scheduled meetings).

8.4 Reporting Procedures

8.4.1 Serious Adverse Events

All unexpected SAEs that result in death or are otherwise reportable SAEs or AEs will be reported promptly to the Data Safety Monitoring Board (DSMB) within 1 business day of knowledge of the event.

AEs (serious or nonserious) that transpire secondary to an overdose must also be reported to the DSMB within 1 business day of knowledge of the event, using an AE form.

The SAE form will always be completed as thoroughly as possible with all available details of the event, signed by the investigator (or designee), and forwarded to the DSMB within the designated time frames. If the investigator does not have all information regarding an SAE, he/she will not wait to receive additional information before notifying the DSMB of the event and completing the SAE form. The form will be updated when additional information is received.

The investigator will always provide an assessment of causality at the time of the initial report.

8.5 AE/SAE Data Collection

When an AE/SAE is suspected, it is the responsibility of the investigator(s) to review all documentation (e.g. hospital progress notes, laboratory and diagnostic reports) relative to the event. The investigator will then record all relevant information regarding a suspected AE/SAE on the AE form. The investigator will attempt to establish a diagnosis of the event based on signs, symptoms, and/or other clinical information. In such cases, the diagnosis should be documented as the AE/SAE and not the individual signs/symptoms.

8.6 The Data and Safety Monitoring Board (DSMB)

The DSMB is composed of members who are independent from the study operations, in compliance with the FDA guidance document (OMB control No. 0910-0581).

For this study, the DSMB is composed of a coordinator and 5 voting members, including a cardiologist from University of Florida in Jacksonville, Florida, a heart failure specialist, a general cardiologist, an infectious disease specialist, and a general internal medicine specialist. The DSMB will meet every 6 months or sooner in case of unanticipated serious adverse events. The DSMB coordinator will provide the board members with data regarding screening, enrollment, adverse events and withdrawals, and he/she will not participate in the voting. The board members

may request unblinding at any time. Upon request of the DSMB (following positive vote by 3 or more members), the coordinator will retrieve the randomization code for one or more individual patients (as needed). If necessary the DSMB will inform the investigators of the unblinding of the randomization code, if not necessary the investigators (and the patients) will be kept blinded. The DSMB may request an expert opinion by one or more non-members, however only the DSMB members will vote on any individual issue. The DSMB (following positive vote by 3 or more members) may request temporary or permanent halting of the study (see halting rules), or interruption of treatment of one or more patients. The minutes from each meeting will be distributed to the board members and to the IRB, and not to the investigators unless specifically requested by the DSMB. A brief conclusive statement addressing whether the study should continue as planned or not will be provided to the investigators and the IRB every 6 months. See Appendix – DSMB Chapter.

8.7 Regulatory Reporting

This study is conducted in accordance to the NIH Good Clinical Practice guidelines. An Investigational New Drug use (IND # 119067) from the Division of Cardiovascular & Renal Products, Center for Drug Evaluation & Research, Food & Drug Administration is held by [name]. The study protocol, consent, and Data and Safety Monitoring Plan has been approved by the VCU IRB. The investigator will notify the Virginia Commonwealth University IRB Panel D, the *ad hoc* Data and Safety Monitoring Board, and the FDA of any severe unexpected adverse event. The investigators will provide the NHLBI staff with reports from the DSMB and the IRB in a timely fashion (within 7 calendar days if fatal or life-threatening unexpected, suspected serious adverse reactions; or within 15 calendar days for all non-fatal, non-life threatening unexpected, suspected serious adverse reactions, or within 30 days of receipt of the DSMB or IRB report for all other unanticipated problems or scheduled meetings).

8.8 Type and Duration of Follow-up of Subjects after Adverse Events

All AEs and SAEs will be followed until resolution, until the condition stabilizes, until the event is otherwise explained, whichever occurs first. All AEs and SAEs documented at a previous visit/contact and designated as ongoing, will be reviewed at subsequent visits/contacts, where the designation may remain ongoing. The investigator will ensure that the follow-up includes any supplemental investigations as may be indicated to elucidate the nature and/or causality of the SAE. This may include additional laboratory tests or investigations, histopathological examinations, or consultation with other health care professionals. SAEs that are ongoing at the time of the subjects final study visit/contact will be documented as ongoing.

8.9 Halting Rules

The DSMB will monitor the progress of the present trial. No interim efficacy analyses are planned; however an interim analysis could be performed at any time to assess efficacy and futility, if requested by the 3 or more members of the DSMB. The DSMB will meet regularly to review safety data every 6 months (or sooner in case of unanticipated serious adverse events). All meetings and actions taken by the committee will be recorded along with the reasons for the actions. These documents will include any data summaries or analyses provided to the DSMB and will remain

confidential until the study is concluded. The DSMB may choose to stop enrollment on the basis of safety data observed. If safety concerns are found, further enrollment will not be allowed until issues are resolved. If no safety concerns are found, enrollment will continue until the target sample size is reached.

9) ADJUDICATION OF CLINICAL EVENTS

